 - iii. COPD assessment - year of diagnosis, home use of supplemental oxygen, self-reported history of spirometry being conducted, number of hospitalizations for COPD exacerbations in the year prior to admission, number of courses of antibiotics and/or steroids for COPD exacerbations in the year prior to admission. For protocol Option 1 this will be collected via self-report utilizing a questionnaire during the hospitalization. For protocol Option 2, this information will be obtained

after discharge and phone consent. For protocol Option 3 as much of this information as possible will be collected from review of the EMR.

- iv. Most recent forced expiratory volume (FEV1) and forced vital capacity (absolute and percent predicted) from EMR if documented in the 3 years prior to admission
- v. Comorbidity assessment to include cardiovascular disease and risk: history of hypertension, hyperlipidemia, coronary artery disease, prior MI, heart failure (ejection fraction prior to admission if available), percutaneous coronary intervention (PCI), coronary artery bypass grafting (CABG), peripheral vascular disease, stroke, diabetes mellitus, cirrhosis, asthma, obstructive sleep apnea, depression, anxiety, end-stage renal disease, cancer (type), organ transplantation (type)
- vi. Respiratory medication use on admission
- vii. Cardiovascular medication use on admission
- viii. Assessment of in hospital MI treatment: thrombolytics, PCI, CABG
- ix. Diagnosis of ST elevation MI (STEMI) or non-ST elevation MI (NSTEMI)
 - x. Initial post MI ejection fraction from inpatient echocardiogram
 - xi. Length of hospital stay
 - xii. Length of ICU stay
 - xiii. Need for intubation
 - xiv. Cardiogenic shock during hospital stay
 - xv. Discharge cardiovascular medications
 - xvi. Discharge disposition
- b. Phone calls (Option 1 only) and EMR review at 3 and 6 months
 - i. Vital status
 - ii. Date and cause of death if applicable
 - iii. Interval history of hospitalization and primary diagnosis (all events will be captured but hospitalizations for COPD exacerbations, recurrent MI, revascularization, or heart failure will be specifically queried)
 - iv. Interval history of treatment with steroids or antibiotics for exacerbations of COPD
 - v. Beta-blocker use and reason for discontinuation, if applicable Medical records will be collected for all admissions

g) Analytic and Statistical considerations.

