- a. Analysis plan for Aim 1. The primary objectives of Aim 1 are to determine the number of admissions per year for AMI at our participating institutions and the prevalence of COPD in that population. These prevalence estimates will be calculated as a simple fraction. We will also compare the clinical characteristics of COPD patients discharged on a beta-blocker versus those not discharged on a beta-blocker using t-tests or chi-square tests (or Fisher's exact tests) as appropriate.
- b. Analysis plan for Aim 2. For the primary analysis we will compare the risk of death or all-cause hospitalization at 6 months for patients with AMI and COPD who were discharged alive on beta-blockers to that of patients not

discharged on beta-blockers. Secondary analyses will include comparisons of rates of hospitalization for COPD exacerbations, rates of hospitalization for recurrent MI or revascularization or heart failure, and rates of treatment with steroids and/or antibiotics for exacerbations. The primary analysis will be based on adjusted Kaplan–Meier survival curves that describe the probability remaining alive and out of hospital in those discharged versus not discharged on beta-blockers, while adjusting for the inverse probability of treatment weighting (IPTW) to reduce confounding. For all time-to-event analyses, the start time will be when the participant is discharged from the hospital.

Participants will be censored at 6 months post-discharge if no event occurred. The comparison of clinical characteristics between treatment groups conducted in aim 1 will be used to inform the calculation of the IPTW. We will use the adjusted log-rank test to compare the two curves. As secondary analyses, we will use both IPTW and adjusted Cox proportional-hazards models to assess the association between the beta-blocker prescription and death or re-hospitalization. Adjusted models will also include the covariates of race, sex, baseline age, smoking status, number of hospitalizations for COPD during the previous year, use of supplemental oxygen, presence of ejection fraction <40% at discharge. Assuming adequate frequencies between groups, we will stratify the models by beta-blocker use at the time of admission, presence of asthma, STEMI vs. NSTEMI, and site. Rates of exacerbation will be analyzed by IPTW negative binomial regression models and will be used to compare annualized rates of hospitalization.

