- c. Sample size and power estimates. Prior data suggests that the prevalence of COPD in patients admitted with acute MI is between 13 and 25% depending on the population studied though these data have depended primarily on administrative coding (13, 16, 26-28). COPD is an independent risk factor for death following MI with estimates of in-hospital mortality of 12.5% versus 8.6% in those without COPD (28). Estimates for 1-year mortality for those with MI and COPD range from 14-25% versus 7-14% in those without COPD (29-33). Estimates of the benefit of beta-blockers in patients with COPD vary widely with studies demonstrating reductions in the risk of mortality between 9 and 50% (4, 13, 15, 16, 34). Data regarding the risk of re-hospitalization in COPD patients with MI and the association with beta-blocker use is scarce. However, the overall rate of readmission for recurrent MI, revascularization, heart failure, serious bleeding, as well as respiratory causes is 1.5-2 fold higher in those with COPD compared to those without the disease with a cumulative risk at 6 months between 25 and 45% (33, 35). Sample size calculations for the proposed study are therefore based on the following assumptions: The estimated sample size (number of patients with COPD and MI) assuming: Risk of death or re-hospitalization at 6 months in patients not prescribed beta blockers – between 32.5 to 37.5%; risk of death or re-hospitalization at 6 months in patients prescribed beta blockers – 25%; proportion of patients discharged on beta-blockers – between 45 and 85%; power of 80%; and type-I error of 5% is given in Table 1. With these assumptions our recruitment target is 500 patients with COPD and MI who

are discharged alive. Assuming in-hospital mortality of 12.5% (28) we plan to consent 571 patients to achieve this goal.

Table 1: Estimated sample size assuming power of 80%, $\alpha=0.05$, and risk of death or re-hospitalization at 6 months of 25% in group receiving beta blockers.

Risk in group not receiving beta blockers	Proportion of patients discharged on Beta-blockers										
	0.4	0.45	0.5	0.55	0.6	0.65	0.7	0.75	0.8	0.85	0.9
0.3	2528	2473	2471	2519	2622	2791	3053	3451	4083	5174	7401
0.325	1139	1119	1122	1148	1200	1283	1409	1600	1901	2420	3478
0.35	648	638	642	660	692	743	819	934	1115	1426	2058
0.375	418	413	417	430	453	488	540	618	741	951	1379

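### The adjusted models enter ejection fraction only as a yes/no cut at 40%, and the IPTW model states no form for it; a continuous term would reduce residual confounding at little cost

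*Combined protocol and SAP*

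**What the plan says.** Section 4(g)(b), the analysis plan for Aim 2, contains two layers of confounding control.

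- **Primary analysis.** Kaplan-Meier curves are compared by an adjusted log-rank test, "while adjusting for the inverse probability of treatment weighting (IPTW) to reduce confounding". The weight model has no list of variables and no functional forms. The plan says only: "The comparison of clinical characteristics between treatment groups conducted in aim 1 will be used to inform the calculation of the IPTW".
- **Secondary analyses.** "As secondary analyses, we will use both IPTW and adjusted Cox proportional-hazards models" are planned. Next comes the covariate list: "Adjusted models will also include the covariates of race, sex, baseline age, smoking status", then further items ending with "presence of ejection fraction <40% at discharge". This is the only form of EF named for any model.

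Section 4(f)(a) lists two EF items for collection. Item x is "Initial post MI ejection fraction from inpatient echocardiogram". Item v covers a history of "heart failure (ejection fraction prior to admission if available". Neither has a cut-off and neither states a recording format. No EF measurement at discharge is listed.

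**The concern.** An indicator for EF below 40% treats a patient at 41% like one at 65%, and a patient at 15% like one at 39%. If prescribing and prognosis vary within those halves, the adjusted comparison still carries that part of the confounding.

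The documents give reason to treat EF as a confounder. The plan itself selects it for adjustment, Section 2 names heart failure as an established indication for beta-blockers, and heart-failure admissions count towards the primary outcome of death or any hospitalization. Bias of this kind does not shrink as recruitment grows. The loss is also avoidable, because the plan collects EF without a cut and discards the gradation only at the modelling step.

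**Working it through.** **1. The plan's own figures.** The documents give no figure for residual confounding, so the sample-size table in Section 4(g)(c) serves only to set the scale. Inputs from that section: 6-month risk "in patients not prescribed beta blockers – between 32.5 to 37.5"%, 25% on beta-blockers, 80% power, and 5% type-I error (two-sided reproduces the table).

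- HR = ln(0.75)/ln(1 − p0): 0.73 at p0 = 0.325 and 0.612 at p0 = 0.375.
- Events = (1.960 + 0.842)² / [s(1 − s)(ln HR)²], where s is the share on beta-blockers.
- N = events / average risk.
- p0 = 0.375, s = 0.5: 7.849/(0.25 × 0.2410) = 130.3 events; 130.3/0.3125 = 417. Table 1 has 417.
- p0 = 0.375, s = 0.7: 155.1/0.2875 = 540. Table 1 has 540.

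At the target of 500 with s = 0.7 and the same risks, events = 500 × 0.2875 = 143.75. The SE of the log HR is 1/√(143.75 × 0.21) = 0.182, before any loss of precision from weighting.

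**2. Share of confounding left by one cut.** Assume EF is normal and acts linearly on prescribing and outcome. Adjusting for the indicator removes the between-half part of the EF variance. The share left is

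1 − φ(z)² / [p(1 − p)],

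where p is the proportion below 40%, z is the normal quantile of p, and φ is the standard normal density. The documents do not give p, so it is varied.

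| p (assumed) | φ(z) | Share left |
|---|---|---|
| 0.15 | 0.233 | 57% |
| 0.20 | 0.280 | 51% |
| 0.25 | 0.318 | 46% |
| 0.30 | 0.348 | 42% |
| 0.35 | 0.370 | 40% |
| 0.40 | 0.386 | 38% |

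Expressed as an assumed mean and SD: 40% is left at 45 and 12, 44% at 47 and 12, 51% at 50 and 12, and 39% at 45 and 14.

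**3. Simulation and other shapes.** Each scenario had 1,000,000 patients, no treatment effect, 70% treated and 30% 6-month risk. EF entered only as the indicator, either in a proportional-hazards model or in the weights.

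| Assumed shape | Share left |
|---|---|
| Normal EF, linear effects, p = 0.20 to 0.35 | 39-54% (model), 37-53% (IPTW) |
| Left-skewed EF, linear effects | about 37-40% |
| Effects flatten above the median EF | about 24-28% |
| Prescribing or outcome changes only at 40% | about 0-5% |

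With EF entered in its true form, the null HR came back as 0.99-1.01.

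**4. One illustration on the HR scale.** Assume p = 0.25, linear effects, and 0.5 log-odds (prescribing) and 0.4 log-hazard (outcome) per SD of lower EF. A true null then appears as HR 1.202 unadjusted and 1.085 after the yes/no adjustment. The share left is ln(1.085)/ln(1.202) = 0.0816/0.1840 = 44%, close to the formula's 46%.

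Against the SE in step 1, the bias is 0.0816/0.182 = 0.45 SE. If the true HR were 0.612, power at 500 patients would be Φ(0.4909/0.182 − 1.96) = 77%. With the shift it would be Φ((0.4909 − 0.0816)/0.182 − 1.96) = 61%.

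**The case against.** **Scope.** A reader might infer that the study adjusts for EF only as a dichotomy. The documents do not support that. The list follows the secondary Cox models, and the primary weight model fixes no form. The Aim 1 comparison that informs the weights includes t-tests as well as tests for categories, so a continuous EF in the weights is compatible with the text. The word *also* before the covariate list could extend it to the weighted models; the wording is ambiguous. This narrows the point but does not remove it, since a continuous EF is guaranteed nowhere.

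**Size.** A reader might take 40-50% as a property of this study. It is not, because no EF mean, spread, shape or share below 40% is given. If prescribing or risk truly steps at 40%, the indicator is nearly sufficient. The other covariates, and stratification by MI type and by beta-blocker use at admission (both conditional on adequate frequencies), may absorb part of what remains. This stands, and the size must be given as a range.

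**Direction.** A reader might infer that the cut must hide benefit or suggest harm. That needs lower-EF patients to be prescribed beta-blockers more often and to do worse. The documents do not state the prescribing half, nor do they call EF a main driver. Section 2 raises, for an earlier study, the possibility that healthier patients received the drugs. That remark concerns general health rather than EF, but it warns against assuming a direction.

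**Data.** A numeric format is a reasonable inference from the collected item, but it is not stated. Some reports may give only a range.

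**Conclusion.** The point holds for the adjusted models: the one stated EF term is a cut at 40%, while EF is collected without a cut. For the primary IPTW analysis the gap is different: the plan does not say whether or in what form EF enters.

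Under normality, linear effects and about 20-35% of patients below 40%, about 40-50% of the confounding by EF stays. Over the shapes and shares examined, the range is about 0% to 57%. The bias is upward only on the further assumption that lower-EF patients are treated more often and fare worse. In the one illustration it is 0.45 SE, which is neither negligible nor decisive.

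The recommendation does not depend on where in that range the truth lies. If risk steps at 40%, a flexible term costs little; if risk is graded, the cut leaves avoidable bias. The change should be made.

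**What to change.** In Section 4(g)(b):

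- Replace the indicator in the adjusted Cox models with the collected EF as a continuous term: a 3-knot restricted cubic spline, or linear plus quadratic.
- State that EF enters the propensity model for the IPTW in the same form.
- Keep the 40% cut for description or subgroups only.
- Name the EF measurement. Section 4(f)(a) collects the initial post-MI value, whereas the covariate refers to discharge, and the two must be reconciled.
- Fix these choices before outcomes are examined.

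**Cost.** No new visits, patients or procedures. Either form uses two terms, so it adds one degree of freedom where the indicator is replaced, and two in the weight model if EF would otherwise be absent. Reports that give EF only as a range need a prespecified midpoint rule.

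### The target of 500 meets the plan's own 80% power requirement in only 5 of the 27 Table 1 scenarios it assumes, and no allowance is stated for the weighting used in the primary test

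*Combined protocol and SAP*

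**What the plan says.** Section 4.g.c (Sample size and power estimates) lists these assumptions:

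- "Risk of death or re-hospitalization at 6 months in patients not prescribed beta blockers – between 32.5 to 37.5" per cent;
- "risk of death or re-hospitalization at 6 months in patients prescribed beta blockers – 25" per cent;
- "proportion of patients discharged on beta-blockers – between 45 and 85" per cent;
- power of 80% and type-I error of 5%.

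Table 1 gives the total number of patients for each combination. The target follows directly: "With these assumptions our recruitment target is 500 patients with COPD and MI" who leave hospital alive. The section does not say which cell, or which part of the table, the target rests on. The only inflation is for 12.5% in-hospital mortality, which raises 500 to 571 patients to be consented.

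Section 4.g.b (Analysis plan for Aim 2) bases the primary analysis on adjusted Kaplan–Meier curves, "while adjusting for the inverse probability of treatment weighting (IPTW) to reduce confounding". The test is stated as: "We will use the adjusted log-rank test to compare the two curves". The weights are not yet specified: "The comparison of clinical characteristics between treatment groups conducted in aim 1 will be used to inform the calculation of the IPTW".

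**The concern.** The target sentence presents 500 as the number that follows from the listed ranges at 80% power. Table 1, in the same section, asks for more than 500 over most of those ranges. If 80% power holds only in one corner of the assumptions, a non-significant primary result could reflect low power rather than no association. The plan intends the study to inform the risk-benefit of beta-blockers after MI in COPD and to prepare for a randomized trial, so that distinction matters.

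A second, separate question is whether the table allows for the weighting in the primary test. If it does not, the power at 500 may be lower still.

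**Working it through.** **Inputs (all from section 4.g.c).** Risk on beta-blockers 0.25. Risk off beta-blockers p0 = 0.325, 0.35 or 0.375. Share on beta-blockers q = 0.45 to 0.85 in steps of 0.05. Power 80%, alpha 5% (sidedness is not stated; two-sided reproduces the table). Target N = 500.

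**Step 1: reproduce Table 1.** Schoenfeld's log-rank formula, without any weighting term:

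- HR = ln(0.75) / ln(1 − p0)
- events = (1.960 + 0.842)² / [q(1 − q)(ln HR)²]
- N = events / [0.25q + p0(1 − q)]

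Example, p0 = 0.35 and q = 0.65: HR = 0.668 and ln HR = −0.404. Events = 7.849 / (0.2275 × 0.1630) = 211.6. Average risk = 0.1625 + 0.1225 = 0.285. N = 211.6 / 0.285 = 742.6, and Table 1 prints 743. The formula matches all 44 cells of the table to within 1 patient. The consent figure also checks: 500 / 0.875 = 571.4.

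**Step 2: compare 500 with the table.** Three rows by nine columns fall within the stated ranges, 27 cells in all.

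| Risk off beta-blockers | Table 1 N, q = 0.45 to 0.85 | Cells with N ≤ 500 |
|---|---|---|
| 32.5% | 1119 to 2420 | 0 of 9 |
| 35% | 638 to 1426 | 0 of 9 |
| 37.5% | 413, 417, 430, 453, 488, 540, 618, 741, 951 | 5 of 9 |

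So 500 is enough in 5 of 27 cells. The other 22 need 540 to 2420. The cell in the middle of both ranges (35%, 65% on beta-blockers) needs 743.

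**Step 3: unweighted power at N = 500.** Power = Φ( √{500[0.25q + p0(1 − q)] q(1 − q)} × |ln HR| − 1.96 ).

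Same example: √(500 × 0.285 × 0.2275) = 5.694; 5.694 × 0.4037 = 2.299; 2.299 − 1.960 = 0.339; Φ(0.339) = 63%.

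| Risk off beta-blockers | 45% | 50% | 55% | 60% | 65% | 70% | 75% | 80% | 85% |
|---|---|---|---|---|---|---|---|---|---|
| 32.5% (HR 0.732) | 47 | 46 | 46 | 44 | 42 | 39 | 35 | 30 | 25 |
| 35% (HR 0.668) | 70 | 70 | 68 | 66 | 63 | 59 | 54 | 47 | 38 |
| 37.5% (HR 0.612) | 87 | 87 | 86 | 84 | 81 | 77 | 71 | 63 | 53 |

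(Columns: share discharged on beta-blockers. Entries: power in %.) Power is 81–87% in the five adequate cells and 25–77% in the other 22; 11 cells are below 50%.

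**Step 4: risk off beta-blockers needed for 80% power at N = 500.** Solving the step 3 expression for p0:

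| On beta-blockers | 45% | 50% | 55% | 60% | 65% | 70% | 75% | 80% | 85% |
|---|---|---|---|---|---|---|---|---|---|
| Risk needed | 36.3% | 36.4% | 36.6% | 36.9% | 37.3% | 38.0% | 39.0% | 40.5% | 42.9% |

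From 70% on beta-blockers upward, the risk needed lies above the assumed ceiling of 37.5%.

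**Step 5: room for weighting.** The variance inflation that each adequate cell can absorb is 500 divided by its Table 1 entry: 500/413 = 1.21, 500/417 = 1.20, 500/430 = 1.16, 500/453 = 1.10, 500/488 = 1.02. The documents give no inflation factor, and none can be derived while the weights are undefined. As an assumption only, five cells keep 80% power at a factor of 1.0, four at 1.1, one at 1.2 (45% on beta-blockers, 80.4%) and none above about 1.21.

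**The case against.** The strongest reply is that nothing has been miscalculated. Table 1 is correct, it sits directly below the target sentence, and it even shows cells less favourable than the stated ranges. On this view the ranges are inputs to the table, and a table running to 2420 cannot be read as a promise that 500 suffices throughout; only a sentence naming the scenario is missing. It is true that the arithmetic is right and that the required N per cell is disclosed. But the table gives neither the power at 500 nor the chosen cell, and the target is expressly tied to the full set of assumptions with no feasibility reason offered.

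The count of 5 in 27 also gives equal weight to arbitrary grid steps, and the plan names no central case. That is fair. The row result does not depend on the count, however: at 35% risk or below, no cell in the stated ranges is met.

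The section also cites a 6-month cumulative readmission risk of 25–45% in COPD, so risks of 38–43% are not outside its own evidence. That figure is not split by beta-blocker use, and the plan chose 37.5% as its ceiling, so it does not support 500 as derived.

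On weighting, adjustment for prognostic covariates can gain precision as well as lose it, and the fall from four cells to one at a factor of 1.2 is partly a knife-edge: the 50% cell has 79.98% power. Both points stand. They limit what can be said to this: no allowance is stated, and the adequate cells have little slack.

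Finally, the study is observational and minimal-risk, and the shortfall neither biases the estimate nor inflates type-I error. True, but it has a primary hypothesis test with a stated power, and that power conflicts with the plan's own table.

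**Conclusion.** The concern holds. The target of 500 gives 80% power only when the risk off beta-blockers is near the top of the assumed range and no more than about 65% of patients go home on a beta-blocker. Elsewhere in the stated ranges it falls short, down to 25% power. These figures take the plan's 25% risk on beta-blockers as given and use a two-sided unweighted log-rank test, which is the calculation that reproduces Table 1. The 571 to be consented does not rescue the claim: it includes the expected in-hospital deaths, and even 571 would reach the tabulated N in only 6 of the 27 cells.

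The weighting point is narrower. The calculation behind the table has no weighting term while the primary test is weighted, and no allowance is stated. The size of any loss is unknown. The power statement for the primary endpoint is wrong as written and must be corrected.

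**What to change.** Keep the target of 500 and correct the claim attached to it in section 4.g.c:

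1. Name the scenario on which 500 rests.
2. Replace the target sentence with wording such as: *500 patients discharged alive give at least 80% power, before any loss from weighting, only if the risk off beta-blockers is at least about 36.3% (45% on beta-blockers) to 37.3% (65% on beta-blockers). At 70% or more on beta-blockers, 80% power requires a risk above the assumed range (about 38.0% at 70%, 39.0% at 75%, 42.9% at 85%). Over the stated ranges, unweighted power is 25–87%.*
3. Add a table of power at N = 500 over the stated ranges, with a sensitivity column for IPTW variance inflation labelled as an assumption, for example 1.0, 1.1, 1.2 and 1.5.
4. State that a non-significant primary result will be interpreted from a confidence interval, and name the estimate it belongs to, such as the IPTW 6-month risk difference or the IPTW Cox hazard ratio. Section 4.g.b attaches no effect estimate to the primary log-rank test, so if the risk difference is chosen this adds a reported quantity.

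The cost is protocol wording and one table. No extra patients are needed, and the endpoint and primary test stay as they are. The downside is that the stated power becomes less favourable.
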